11.4 Interval Windows

The study windows are presented in the Time and Event Schedule (Section 1.1).

For analysis purposes, the baseline/screening evaluation is to be done within 30 days prior to the first injection; the first injection is considered to be day 0. The 2, 4, 8, 16 and 26 week visits will occur in the time intervals (days) indicated in the following table:

Study Interval Windows [days]						
Baseline/ Screening	Injection	2 Week	4 Week	8 Week	16 Week	26 Week
-30 to 0	Day 0 (by definition)	11 to 17	21 to 35	46 to 74	105 to 134	159 to 201

11.5 Handling of Missing Data

The primary efficacy endpoint analysis will be conducted on the modified intent to treat (MITT) analysis set, which consists of all primary endpoint data on all As Treated subjects (regardless of whether or not there were protocol deviations associated with the data) for the 2, 4, 8, 16 and 26 week visits. In this MITT Analysis Set, primary endpoint data for the 26 week visit will be imputed with multiple imputation methodology (missing primary endpoint data for the 26 week visit will be imputed).

A supportive primary endpoint analysis will be conducted on the Per Protocol Analysis Set for Longitudinal Analysis, with no imputation for missing data. Aside from any other sensitivity analysis purposes, all other analyses will utilize only actual subject data which are collected; no imputation of missing data will be performed.

11.6 Endpoints

Primary Endpoint:

The primary efficacy endpoint in this study is the WOMAC A1 (walking pain) score (response options 0 through 10, where 0 indicates no pain and 10 indicates worst possible pain) change from baseline at 26 weeks.

The primary efficacy analysis is a superiority comparison of MONOVISC vs. saline in WOMAC A1 pain score change from baseline at 26 weeks. The primary endpoint analysis will be based upon a longitudinal model of all primary endpoint data from 2 weeks through 26 weeks; the adjusted means at 26 weeks from this longitudinal model at 26 weeks will be compared.

Secondary Endpoints:

- WOMAC A1 Pain change from baseline at the 2, 4, 8, and 16 week time points as measured by WOMAC A1 pain score.

Tertiary Endpoints:

- Walking pain at the 2, 4, 8, 16 and 26 week time points as measured by WOMAC A1 score.
- Area-under-curve (AUC) analysis of walking pain change from baseline using longitudinal model over time comparing treatment vs. control.
- Pain at the 2, 4, 8, 16 and 26 week time points as measured by WOMAC A (pain) score.
- Pain improvement from baseline at the 2, 4, 8, 16 and 26 week time points as measured by WOMAC A (pain) score.
- Total WOMAC (pain, function, stiffness) score at the 2, 4, 8, 16 and 26 week time points.
- Improvement from baseline in Total WOMAC (pain, function, stiffness) score at the 2, 4, 8, 16 and 26 week time points.
- OMERACT-OARSI responder rate at the 2, 4, 8, 16 and 26 week time points.
- Patient Global Assessment (PGA) at the 2, 4, 8, 16, and 26 week time points.
- SF-12 outcomes at study defined time-points
- Rescue medicine consumption (acetaminophen) from baseline through week 26

Safety:

- Safety of the therapy will be assessed by comparing the incidence of adverse events in the treated vs the control group through 26 weeks post-injection, including AEs that occur during injection.

11.7 Hypotheses

The primary endpoint analysis will be to demonstrate that the mean WOMAC A1 pain change from baseline for MONOVISC is significantly better than the mean WOMAC A1 pain change from baseline for Saline at 26 weeks after the first injection. The null (H_0) and alternate (H_A) hypotheses for this test of superiority are as follows:

$$H_0: \mu_{\text{MONOVISC}} \geq \mu_{\text{Saline}}$$

$$H_A: \mu_{\text{MONOVISC}} < \mu_{\text{Saline}},$$

where μ_{MONOVISC} is the mean WOMAC A1 pain change from baseline for MONOVISC at 26 weeks, and μ_{Saline} is the mean WOMAC A1 pain change from baseline for Saline at 26 weeks.

Decision Criterion: The primary endpoint analysis will be based upon a longitudinal model of all primary endpoint data from 2 weeks through 26 weeks; the adjusted means at 26 weeks from

this longitudinal model at 26 weeks will be compared. The decision will be made to reject the null hypotheses H_0 and conclude the alternative hypothesis H_A if the WOMAC A1 pain change from baseline adjusted mean for MONOVISC is less than the WOMAC A1 Pain change from baseline adjusted mean for Saline at 26 weeks, and the two sided p-value for the comparison of these adjusted means at 26 weeks is less than 0.05, or equivalently, if the entire 2-sided 95% confidence interval for the WOMAC A1 pain change from baseline adjusted mean difference (MONOVISC minus Saline), based upon the longitudinal model estimates, is less than 0. This primary efficacy endpoint analysis will be conducted on the MITT analysis set.

11.8 Analysis Sets

A detailed accounting of all enrolled Subjects will be documented with the following analysis sets.

Intent to Treat (ITT) Analysis Set

The Intent to Treat (ITT) Analysis Set consists of all subjects who are enrolled into the study. subjects in the ITT dataset but in whom treatment is not attempted with either MONOVISC or saline will be listed along with the reason for not being treated.

Safety Analysis Set

The Safety Analysis Set consists of all randomized subjects who are enrolled into the study, in whom treatment is attempted with either MONOVISC or saline. Subjects will be analyzed according to the treatment which is attempted.

As Treated (AT) Analysis Set for Each Study Defined Time Point

For each follow-up time point (the 2, 4, 8, 16 and 26 week visits), the As Treated (AT) Analysis Set (for the interval) will consist of all Safety Analysis Set subjects who have a follow-up visit within the interval in which WOMAC A1 pain data were collected. Reasons for not having WOMAC A1 pain follow-up in the interval will be documented (including deaths, withdrawals of consent, and Subjects who are past due for follow-up in the interval).

Modified Intent to Treat (MITT) Analysis Set (for Longitudinal Analysis)

All primary endpoint data from all As Treated Analysis Sets for the 2, 4, 8, 16 and 26 week visits will be combined into a dataset upon which longitudinal analysis for the primary endpoint can be conducted. In this MITT analysis set, primary endpoint data for the 26 week visit will be imputed with multiple imputation methodology.

Per Protocol (PP) Analysis Set for Each Study Defined Time Point

[figure not shown]
For each follow-up time point (the 2, 4, 8, 16 and 26 week visits), the Per Protocol (PP) Analysis Set (for the interval) will consist of As Treated Analysis Set subjects (for the interval), excluding protocol violations which are deemed to have possibly affected the scientific validity of the data. Note that some subjects may have data excluded from a particular Per Protocol Analysis Set for an interval (for example, if they used acetaminophen within 48 hours prior to a study visit), or from all Per Protocol Analysis Sets for all intervals (for example, if they failed an inclusion/exclusion criterion that is deemed to possibly affect the scientific validity of the data).

Per Protocol Analysis Set for Longitudinal Analysis

All primary endpoint data from all Per Protocol Analysis Sets for the 2, 4, 8, 16 and 26 week visits will be combined into a dataset upon which longitudinal analysis for the primary endpoint can be conducted.

For each follow-up time point, a flowchart as depicted below will be created. This flowchart will present the Safety Analysis Set, the As Treated Analysis Set for the interval, and the Per Protocol Analysis Set for the interval. This diagram will indicate all protocol violations, deaths, withdrawals of consent, and Subjects who are past due for follow-up in the interval.

Flow Diagram for []-Week Study Interval

A Medically Trained Professional and a Biostatistician at DePuy Synthes will review and confirm all protocol non-compliances prior to the planned interim analysis (if possible), and also prior to final dataset lock.

11.9 Sample Size Justification

The sample size was determined based on the primary endpoint, which is a superiority comparison of WOMAC A1 pain change from baseline at 26 weeks for MONOVISC Subjects compared to Saline Subjects. Although it is planned to conduct the primary endpoint analysis with a longitudinal model, and to compare the WOMAC A1 pain change from baseline adjusted means at 26 weeks from this longitudinal model, the sample size was established based upon estimates for a t-test comparison of 26 week means for simplicity. Specifically, it is anticipated that the mean difference in WOMAC A1 pain change from baseline means will be at least 0.6 (where the mean for MONOVISC subjects is less than the mean for Saline Subjects), and that the standard deviation in WOMAC A1 pain change from baseline at 26 weeks will be approximately 2.2 in both groups. This standard deviation of 2.2 is consistent with published studies by Spitzer (2010) and Qvistgaard (2006); also, 2.2 is approximately $\frac{1}{4}$ of the maximum anticipated range of WOMAC A1 pain change from baseline, which would be an estimate of the standard deviation from data which are normally distributed. Using a two-tailed t-test and assuming a 2:1 randomization, the required sample size to yield 80% statistical power was estimated to be 318 MONOVISC and 159 Saline. With an anticipated attrition rate of 15%, the total study population was increased to be 560 patients (374 MONOVISC, 186 Saline). The sample size estimate was calculated with the following SAS code:

SAS Code for Power Estimation:
WOMAC A pain at 26 weeks

```
proc power;
  twosamplemeans
  meandiff= .6
  stddev=2.2
  groupweights=(2 1)
  power= .8
  alpha=0.05
  sides=2
  ntotal=.;
run;
```

The primary efficacy endpoint analysis will be conducted on the modified intent treat (MITT) Analysis Set with the handling of missing data at 26 weeks as described in Section 11.5 above. A supportive analysis will be conducted on the Per Protocol Analysis Set for Longitudinal Analysis.

11.10 Analysis Plan

All statistical processing will be performed using SAS® Version 9.2 or higher, unless otherwise noted. A separate Statistical Analysis Plan (SAP) document that provides greater detail on data derivations and the analyses to be performed will be developed within 90 days after the first patient is enrolled.

Summary tables will be provided for subject demographics and baseline variables for the Safety Analysis Set, the As Treated Analysis Set at 26 weeks, and the Per Protocol Analysis Set at 26 weeks. Safety endpoints (adverse events) will be summarized on the Safety Analysis Set. Effectiveness endpoints will be summarized at each protocol-specified evaluation time point on the Per Protocol Analysis Set for the time point. Analyses will be conducted on pooled data from all sites. For the primary endpoint data at 26 weeks, a 2-way ANOVA test with interaction term will be conducted to confirm the homogeneity of 26 week data across sites. The primary endpoint analysis will be conducted with a longitudinal model on the MITT Analysis Set using PROC MIXED and an antedependence covariance structure to model the correlation between visits. A supportive analysis of the primary endpoint analysis will be conducted on the Per Protocol Analysis Set for Longitudinal Analysis with the same PROC MIXED model.

Descriptive statistics for dichotomous/categorical variables will include the number and percentage of subjects. Fisher's exact test 2-sided *p*-values will be provided for the comparison of dichotomous variables, including adverse event rates, to facilitate clinical judgment. Descriptive statistics for continuous variables will include the number of subjects, mean, standard deviation, median, minimum, and maximum. *P*-values for comparing continuous endpoints will be provided to facilitate clinical judgment; these will be 2-sided *p*-values based upon the t-distribution.

If Age, Gender, or pre-injection WOMAC A1 pain score are found to be significantly different (*p*<0.05) across treatment groups in the As Treated Analysis Set at 26 weeks, then an ANCOVA sensitivity analysis will be conducted for the primary endpoint analysis (on the MITT Analysis Set, with Age, Gender, and pre-injection WOMAC A1 pain as covariates).

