6.2 Injection Regimen

The intra-articular HA injection regimen in the present study represents a departure from conventional HA dosing. Rather than a single injection of HA or a series of weekly HA injections, a regimen of *two (2) HA injections separated by one (1) month* will be implemented in this study.

Injections must be given using image guidance to insure delivery of MONOVISC into the hip joint. Either ultrasound or fluoroscopy may be used. ***However, each site should use the same image guidance method for all patients treated at that site.***

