11.2 Treatment Assignment

The treatment groups in this study are:

MONOVISC: Two intra-articular injections of MONOVISC High Molecular Weight Hyaluronan, separated by 1 month (active treatment).

Saline: Two injections of 4 ml saline, separated by 1 month (control treatment).

Subjects will be randomized in a 2:1 ratio to receive either treatment with MONOVISC or treatment with Saline. Block randomization (random blocks of size 3 or 6) will be used to create a Master Randomization List, and patient kits of MONOVISC and saline will be sequentially numbered according to this list. With this randomization scheme, each study subject will be associated with a unique kit number, and the order of randomized subjects at each investigational site will be distinct. Prior to initiation of the study, investigational sites will be provided with an initial, sequentially numbered quantity of kits to be used, and as these kits are utilized, additional quantities of sequentially numbered kits can be ordered as needed through an electronic re-order system. The kit will not contain any labeling to indicate whether the patient is receiving MONOVISC or Saline. After the first injection, the remaining syringe will be returned to the storage site for the second injection.

All clinical research and biostatistics personnel at DePuy Synthes Mitek Sports Medicine will remain blinded to treatment assignment until the end of the study. An employee within Strategic Medical Affairs will be designated to maintain the Master Randomization, to facilitate any medical safety reviews, if necessary, and to facilitate the planned interim futility analysis.

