13.4 Efficacy Evaluations

13.4.1 Primary Endpoint Analyses

The primary endpoint analysis will be conducted with a longitudinal model on the MITT Analysis Set using PROC MIXED. The model will include absolute change from baseline in WOMAC A1 as the dependent variable, treatment (MONOVISC versus Saline) and visit (Week 2, Week 4, Week 8, Week 16, and Week 26) as fixed effects, and subject as a random effect. In the model, visit will be treated as class variable and an antidependence covariance matrix will be assumed to model the within-subject variability between visits. The antidependence structure allows the correlation between different time periods to vary. Denominator degrees of freedom will be estimated using the Kenward–Roger approximation.

In order to test the robustness of study results to the antedependence model assumptions, the primary endpoint longitudinal analysis will be repeated with two additional covariance structures: autoregressive (AR) and Toeplitz. These analyses will be conducted on the same MITT analysis set which was utilized for the primary endpoint analysis.

With a mixed effects model as the primary analysis model, no imputation of missing data at visits prior to the Week 26 will be done. However, missing data at Week 26 will be imputed, as discussed in Section 8. A supportive analysis of the primary endpoint analysis will be conducted on the Per Protocol Analysis Set for Longitudinal Analysis with the same longitudinal model.

Age, Gender, and pre-injection WOMAC A1 pain score will be compared between treatment groups and if they are found to be significantly different ($p<0.05$) in the As Treated Analysis Set at 26 weeks, then an additional sensitivity analysis will be conducted for the primary endpoint analysis. In this analysis, fixed effects for Age, Gender, and the continuous baseline value of WOMAC A1 will be added, but otherwise the model will remain the same.

If marked differences are observed between the results obtained with the primary longitudinal model and any of the sensitivity analysis, they will be reported and addressed in the Clinical Study Report.

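### The primary model has no site term, and site can reach the primary inference only through a data-dependent switch; a prespecified random site intercept would recover a little precision and remove the switch

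*Protocol*

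**What the plan says.** **Allocation.** Protocol 11.2: "Subjects will be randomized in a 2:1 ratio to receive either treatment with MONOVISC or treatment with Saline". One master list is built in random blocks of 3 or 6. Before the study starts, "investigational sites will be provided with an initial, sequentially numbered quantity of kits to be used", and later re-orders are sequential too. Under Protocol 8.5.1 the injector takes the next numbered kit. SAP Table 1 records that stratifying by site was judged not feasible for supply reasons.

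**Primary model.** SAP 13.4.1 takes change in WOMAC A1 as the outcome, with "treatment (MONOVISC versus Saline) and visit (Week 2, Week 4, Week 8, Week 16, and Week 26) as fixed effects" and subject as random. Site is absent. The secondary endpoints use the same model (SAP 13.4.2).

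**Where site does appear.** Protocol 11.10 states that "Analyses will be conducted on pooled data from all sites" and adds a two-way ANOVA with interaction as a homogeneity check (also SAP 13.6). SAP 13 makes pooling conditional on the outcome of SAP 13.7. That section refits the longitudinal model with site and treatment-by-site, pooling sites with fewer than 10 subjects. If the overall site effect is significant, a stratified analysis takes the place of the primary analysis for the primary and secondary endpoints, and the analyses are run by site.

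**A possible source of site differences.** Protocol 6.2 says "each site should use the same image guidance method for all patients treated at that site", so ultrasound or fluoroscopy is confounded with site.

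**The concern.** When allocation is balanced within sites, a difference in average response between sites largely cancels out of the treatment comparison. A model without site still counts that variation as noise, so its standard error overstates the real spread of the estimate and some power is lost.

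The route by which site can enter is also a weak one. A site main effect says that average response differs between sites; it does not say that the treatment difference does. Yet under SAP 13.7 a significant overall site effect is enough to displace the single prespecified comparison. At stake are a small amount of precision in the deciding test and in the gatekept secondaries, and certainty about which analysis decides the trial.

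**Working it through.** **1. The plan's own figure.** Protocol 11.9 assumes that "the mean difference in WOMAC A1 pain change from baseline means will be at least 0.6", that the SD "will be approximately 2.2 in both groups", two-sided alpha 0.05 and 2:1 allocation; "the required sample size to yield 80% statistical power was estimated to be 318 MONOVISC and 159 Saline".

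- SE = 2.2 × √(1/318 + 1/159) = 0.2137
- Power ≈ Φ(0.6/0.2137 − 1.96) = Φ(0.848) = 80.2%; the noncentral t gives 80.0%

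The figure reproduces, with no site term.

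**2. Assumptions the documents do not supply.** The site ICC is varied from 0 to 0.10 within a total SD of 2.2. Kit shipments are runs of 3 to 24. Sites number 25 (SAP 4) or 40 (Protocol 6.0). Attrition is 15% (Protocol 11.9), taken as random. Only week 26 is modelled.

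**3. How much balance the kit supply gives.** Let a_j = n1j/n1 − n0j/n0 be site j's imbalance. The share of the between-site contribution removed is B = 1 − Σa_j² / (1/n1 + 1/n0). Simulating the blocked list dealt to sites in consecutive runs:

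- at randomisation, B = 56–92%
- after 15% attrition, B = 48–79%
- under simple randomisation, for comparison, B = 2–6%

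**4. Effect on the pooled standard error.** True SE / model SE = √(1 − ICC × B). With 40 sites and runs of 6:

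- ICC 0.05, B = 0.633: √(1 − 0.0317) = 0.984; actual type I error 2[1 − Φ(1.96/0.984)] = 0.046
- ICC 0.10, B = 0.625: √(1 − 0.0625) = 0.968; actual type I error 0.043

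**5. Power with and without site.** Without site, power = Φ((0.6 − 1.96 × model SE)/true SE). With a random intercept, it is Φ(0.6/SE_GLS − 1.96), where SE_GLS comes from generalised least squares with the site variance taken as known. For 40 sites, runs of 6 and 15% attrition:

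| ICC | No site | Fixed site | Random intercept | Gain, random vs none |
|---|---|---|---|---|
| 0 | 80.1% | 78.6% | 80.1% | 0.0 |
| 0.02 | 80.2% | 79.4% | 80.6% | 0.4 |
| 0.05 | 80.5% | 80.7% | 81.6% | 1.1 |
| 0.10 | 80.9% | 82.7% | 83.4% | 2.5 |

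Simulations that estimate the site variance by REML, over other site counts and run lengths, widen the gain to about 1–1.6 points at 0.05 and 2–3 at 0.10. They show no material loss at 0 (within 0.2 point), and coverage stays at about 94–96%.

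**6. How often the SAP 13.7 switch would fire.** Take a 5% F-test for site at week 26 with J equal sites and n = 477/J per site. The F statistic is inflated by r = 1 + n × ICC/(1 − ICC), so P(trigger) = P(F > F_crit/r). At ICC 0.05, r = 1.63 (40 sites) or 2.00 (25 sites).

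| ICC | 40 sites | 25 sites |
|---|---|---|
| 0 | 0.05 | 0.05 |
| 0.02 | 0.26 | 0.33 |
| 0.05 | 0.68 | 0.78 |
| 0.10 | 0.97 | 0.98 |

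With unequal sites and those under 10 pooled, the probabilities are similar: 0.65–0.80 at 0.05 and 0.93–0.98 at 0.10.

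**7. What by-site analysis would mean if read literally.** With 25 equal sites, the SE per site is 0.2137 × √25 = 1.07, and 0.6/1.07 = 0.56 against the 1.96 needed. No single site could test the planned difference.

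**The case against.** - **SAP 13.7 already deals with site.** A reader might infer from Protocol 11.10 and SAP 13.4.1 that site is never used for the deciding test. The documents do not support that: SAP 13 and 13.7 replace the pooled analysis when the site effect is significant, and this is likely at ICC 0.05 or more, where the gain is largest. The power gains above are therefore relative to an always-pooled analysis, which is not quite what the SAP plans. This stands. The switch is no substitute, though. It names no level of its own (the general 5% of SAP 6 is the natural default), it depends on the data, and it leaves open whether one combined estimate or a set of site results decides.
- **The balance is accidental.** True. It follows from kit supply, attrition erodes it, and the shipment size is not stated.
- **Adjusting for site can cost power.** True for fixed site effects at low ICC (78.6% against 80.1% at ICC 0), but not materially for a random intercept.
- **The check is not the planned model.** It omits the five visits, the antedependence covariance and the week-26 imputation, and a single intercept assumes the same site effect at every visit. That stands as a limit on the figures.
- **Nothing shows that sites differ.** Also true. Guidance method is a possible reason, not evidence.

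**Conclusion.** The concern holds as a low-cost improvement, not as a flaw that invalidates the trial. The primary model omits site although allocation is roughly balanced by site. If sites differ, the pooled test is slightly conservative: type I error is about 0.046 at ICC 0.05 and 0.043 at 0.10 with 40 sites and runs of 6. The power forgone against an always-pooled analysis is nil at ICC 0, under 1 point at 0.02, 1–1.6 at 0.05 and 2–3 at 0.10.

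A reader might infer that the trial is underpowered. It is not on this account: the 80% was calculated without a site term, and it reproduces.

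The more practical weakness is that site enters the primary inference only through a rule that depends on the data and has no clear single estimate as its result. All sizes rest on an assumed ICC, assumed shipment sizes, random attrition, a week-26 approximation and, for the trigger, a 5% level.

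**What to change.** - **Protocol 11.10 and SAP 13.4.1:** add a random site intercept (in PROC MIXED, RANDOM intercept / SUBJECT=site) to the primary longitudinal model and to its per-protocol, covariance-structure and covariate repeats. Fit it whatever any site test shows, and report one overall MONOVISC-minus-Saline estimate. The secondary endpoints inherit the change.
- **SAP 13 and 13.7:** state that the site and treatment-by-site analyses are sensitivity or descriptive only and never replace the primary analysis. Without this edit the switch would still override the new model.

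The cost is wording in these sections, one extra statement in the code and one extra variance parameter, with no added data or patients. If the site variance is estimated as zero, the planned result is recovered. The change should be made before treatment codes are linked to outcomes.
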